1.4 Rationale for use in recurrent glioblastoma

Approximately 22,850 people are diagnosed with primary cancer of the nervous system every year leading to 15,320 deaths (1). Glioblastoma is by far the most common type of primary brain cancer. The 5-year survival rate for patients with glioblastoma is 3.3% substantiating the great need for improved therapy (1). Following first recurrence, progression free survival with second-line therapy at six months (PFS6) is about 15%. Immunotherapy is one promising option for patients with glioblastoma and a number of forms of active specific vaccination have been devised and are being investigated this cancer. These include both cellular therapies and peptide conjugates such as rindopepimut (Rintega) (2). The latter provides active specific vaccination to EGFRvIII, which is expressed by only about 30% of glioblastomas (3).

Survivin is a common cancer-associated protein that is immunologically targetable (4). It is expressed by at least 90% of human glioblastomas and by many other non-CNS cancers as well (5). SVN53-67/M57-KLH (SurVaxM) is long survivin peptide mimic that has enhanced binding to HLA-A*02 molecules (4, 6). SurVaxM has been tested at a fixed dose of 500 µg in a first-in-man study to assess safety, tolerability and immunologic effects in patients with recurrent malignant glioma following failure of standard therapy. In that study, SurVaxM was given in emulsion with Montanide ISA 51 together with sargramostim (GM-CSF) to a total of 9 patients. The vaccine was well-tolerated. Mild (grade I) injection site reactions were common, but no serious adverse events due to the vaccine were observed. All evaluable patients developed survivin-specific CD8+ T cell responses and antibody titers to the survivin peptide and to the conjugated carrier protein KLH. Evidence of specific cytokine-mediated helper support was also observed. Median overall survival was 68 weeks from trial entry (7). This phase I study was followed by a multi-center phase II clinical trial of SurVaxM in combination with standard therapy (Stupp protocol) in patients with newly diagnosed glioblastoma being conducted at five institutions. An interim analysis of data from the first 55 patients was conducted. Patients ranged in age from 20-82 years (median = 60), male:female = 38:25 with survivin tumor expression of 1-40% (median = 12%) by immunohistochemistry. PFS-6 was 96.3% (n=55) measured from diagnosis and 62.8% (n=43) from first immunization. OS-12 was 90.9% (n=33) from diagnosis and 70.8% (n=24) from first immunization. As in the phase I study, the regimen was generally well tolerated and immunization-related adverse events were mild with no serious adverse

Version 9: 1-Nov-2017

events directly attributable to SurVaxM. The vaccine was highly immunogenic and produced survivin-specific antibody (IgG) titers and CD8+ T-cells detectable by survivin dextramers.

Glioblastoma is known to be an immunosuppressive cancer and the microenvironment of these tumors is not highly permissive for CD8-mediated tumor cell killing (8). In addition, these tumors secrete substances that suppress systemic anti-tumoral immunity. Following surgical resection of bulk disease immune responses improve substantially. Therefore, immunotherapy is more likely to be effective in such patients following reduction of bulk disease by surgical resection. In one study of over 1,200 glioma patients, PD-1 expression on tumor-infiltrating lymphocytes was detected in 48% of gliomas and was higher in glioblastoma than in lower grade gliomas (54% vs. 30%, p = 0.005)(9). In addition, PD-L1 expression on tumor cells was seen in 27% and was more common in tumors with unmethylated MGMT promoters (36% vs. 18%, p = 0.01), which is the group of glioblastoma patients in greatest need of improved therapies (9). It is likely that PD-1 and PDL-1 expression are even higher in patients with recurrent malignant gliomas. Therefore, immune checkpoint blockade with anti-PD-1 could potentiate the effect of vaccines in such individuals.

Since there have been relatively few trials of immune checkpoint inhibitors in glioblastoma patients to date, particularly those in which PEM is combined with specific cancer vaccines, there are a number of unanswered question that the proposed study can begin to address. A fundamental question is whether PD-1 inhibitors will be more effective when combined with active specific vaccination against a common cancer antigen, such as survivin. First, it will be important to study the combination of SurVaxM and PEM to assess safety, tolerability and toxicity. Second, we plan to measure the immunologic effects of the vaccine when given together with PEM and compare those results to our first-in-man study of SurVaxM in patients with recurrent malignant glioma. Third, we plan to assess potential clinical activity of the drug combination to see if any radiologic responses are evident and to measure the effects on PFS, compared to reported historical patient cohorts with recurrent glioblastoma. Since there is ongoing study of Nivolumab in patients with newly diagnosed glioblastoma, this proposed study will allow patients who have failed previous anti-PD1 blockade to be treated with the combination of anti-PD1 and SurVaxM. These patients will be studied in a separate exploratory cohort.

Version 9: 1-Nov-2017

2.0 OBJECTIVES

2.1 Primary **Objective**:

1. Assess clinical activity of Pembrolizumab and SurVaxM in patients with recurrent glioblastoma using progression free survival at 6 months (PFS-6) as determined using RANO criteria

Hypothesis:

The combination of Pembrolizumab and SurVaxM improves PFS-6 in patients with recurrent glioblastoma compared to historical controls

2.2 Secondary **Objective(s)**:

- 1. Assess safety and tolerability of Pembrolizumab and SurVaxM in patients with recurrent glioblastoma
- 2. Assess response rates of Pembrolizumab and SurVaxM in patients with recurrent glioblastoma as determined using RANO criteria
- 3. Assess overall survival with the combination of Pembrolizumab and SurVaxM in patients with recurrent glioblastoma
- 4. Assess PFS using Pembrolizumab and SurVaxM in patients with recurrent glioblastoma

Hypothesis:

- 1. The combination of Pembrolizumab and SurVaxM is safe in patients with recurrent glioblastoma
- 2. The combination of Pembrolizumab and SurVaxM produces responses in patients with recurrent glioblastoma
- 3. The combination of Pembrolizumab and SurVaxM improves overall survival in patients with recurrent glioblastoma
- 4. The combination of Pembrolizumab and SurVaxM improves PFS in patients with recurrent glioblastoma

2.3 Exploratory **Objective(s)**:

1. Measure both cellular and humoral immune responses during concurrent administration of Pembrolizumab and SurVaxM in patients with recurrent glioblastoma

Version 9: 1-Nov-2017

- 2. Correlate clinical responses with molecular markers measured on tumor cells (survivin, PDL-1, PDL-2, MGMT and IDH-1) and on peripheral blood mononuclear cells (PD-1)
- 3. Assess response rates of Pembrolizumab and SurVaxM in patients with recurrent glioblastoma as determined using iRANO criteria
- 4. Exploratory analysis of survivin expression and clinical outcome.
- 5. Outcomes in 10 patients with glioblastoma in first recurrence that have progressed on anti PD1 therapy (Arm B).

3.0 STUDY DESIGN

This is a Phase II study of two arms in patients with recurrent glioblastoma. Arm A is patients with first recurrence of glioblastoma who have failed prior chemotherapy and radiation but have not received any immunotherapy. Arm B is an exploratory arm of 10 patients who have failed prior anti-PD1 therapy.

This will be a phase II clinical study with a 10 patient, toxicity run-in. The study follows upon the recently completed clinical study I-171010, entitled: Phase I study of safety, tolerability and immunological effects of SVN53-67/M57- KLH (SurVaxM) in patients with survivin-positive malignant gliomas [1]. All patients will receive the study drug combination consisting of SurVaxM and pembrolizumab (PEM) with no randomization, stratification or dose escalation. The combination of PEM and SurVaxM will be tested in patients with recurrent or progressive glioblastoma following failure of standard therapy. Patients who have developed progressive or recurrent disease following treatment with surgery, fractionated external beam radiation therapy and chemotherapy with temozolomide, and who meet eligibility criteria will be enrolled. All patients must have histologic confirmation of glioblastoma and central neuropathology review of survivin expression by tumor cells. Patients will be followed on-study with regular neurologic and physical exams. While receiving PEM and SurVaxM, blood will be obtained regularly to assess hepatic, renal, electrolytes, adrenal and thyroid function. Immunologic assays will be performed prior to each dose of SurVaxM at induction and every 12 weeks thereafter, and at the off-study evaluation. Patients will be followed for up to 2 years, or until disease progression or death. Patients will be followed closely for regimenlimiting toxicity (RLT) using CTCAE v5.0 parameters. Brain MRI scans will be performed at entry and every 9 weeks thereafter (standard-of-care). Responses and tumor progression will be judged using RANO criteria and PFS6 will be recorded as the primary end-point.

Trial Diagram/Schema

Recurrent glioblastoma Patients

Û

Pembrolizumab + Survax M

MRI every 9 weeks

Treatment until Progression or intolerable toxicity

Completion of pembrolizumab Q3W monotherapy consists of 35 treatments (approximately 2 years)

Version 9: 1-Nov-2017

3.1 Blinding/Unblinding Non-applicable

3.2 Number of Subjects

This study consists of two arms to evaluate the anti-tumor activity of Pembrolizumab and SurVaxM and administered according to standard and reduced dosage schedules in subjects with recurrent glioblastoma.

This clinical trial will use a single stage involving a maximum accrual of 41 patients with glioblastoma at first recurrence (bevacizumabnaïve). This will include a 10-patient toxicity/safety run-in. Patients in the initial run-in will be included in the assessment of response. Patients in the run-in will be followed using CTCAE v 5.0 criteria and if the combination regimen is excessively toxic defined as dose limiting toxicity seen in more than 33% of the patients, the study will be stopped. The probabilities of observing 3, 4, and 5 DLTs out of 10 patients with true toxicity rate of 33% is 23%, 26%, and 13%. If 4 or less DLTs observed in the 10 patients, the study proceed with more patients. If 5 or more DLTs observed, accrual will be suspended and toxicity profile we be fully evaluated.

If toxicity threshold to stop will not be reached, an additional 31 patients will be enrolled for total of 41 patients.

There will an exploratory cohort of 10 patients who have failed prior PD1 blockade that will be treated with the combination of PEM + SurVaxM and results of this arm will be reported in a descriptive manner.

For this purpose, approximately 51 subjects will be enrolled in the two arms of the trial.

Week 1 of each cycle, the subject will receive both Pembrolizumab and the SurVaxM Vaccine. On Week 3 of cycle 1, and Week 2 of cycle 2, the patient will receive the SurVaxM Vaccine alone.

Completion of pembrolizumab Q3W monotherapy consists of 35 treatments (approximately 2 years)

Version 9: 1-Nov-2017

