Interventions- Experimental	Pembrolizumab 200 mg IV every 3 weeks SurVaxM (SVN53-67/M57-KLH) 500 mcg per dose, dosed	

1 0 4 1 1 1 2 1
every two weeks for 4 doses and then every 3 months
Sargramostim (GM-CSF) 100 mcg per dose, dosed every
two weeks for 4 doses and then every 3 months
Montanide ISA 51, 1 ml per dose dosed every two weeks
for 4 doses and then every 3 months

ABBREVIATIONS

ADDINE	VIATIONS
CCCC	Case Comprehensive Cancer Center
CRF	Case Report Form
DCRU	Dahm's Clinical Research Unit
DSTC	Data Safety and Toxicity Committee
FDA	Food and Drug Administration
ICF	Informed Consent Form
IRB	Institutional Review Board
PRMC	Protocol Review and Monitoring Committee
SOC	Standard of Care
CCF	Cleveland Clinic Foundation
UH	University Hospitals

TABLE OF CONTENTS

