6.1 Treatment Regimen Overview

SVN53-67/M57-KLH (SurVaxM)

The synthetic peptide in SurVaxM (SVN53-67/M57) spans amino acids 53 through 67 of the mature human (and mouse) survivin protein sequence and contains a substitution of methionine

(M) for cysteine (C) at position 57 which leads to enhanced MHC class I binding. The peptide is

Version 9: 1-Nov-2017

conjugated to Keyhole Limpet Hemocyanin (KLH). SVN53-67/M57-KLH contains a peptide mimic that is immunogenic in humans and in C57BL/6 mice. The planned investigational study is based on extensive experimental observation concerning the ability of SurVaxM to elicit potent

and specific immune responses that are capable of inhibiting the growth of cerebral gliomas in mice and killing human glioma cells ex vivo via cytotoxic T lymphocyte (CTL) activity.

The investigational product should be stored in a secure area according to local regulations. It is the responsibility of the investigator to ensure that investigational product is only dispensed to study subjects. The investigational product must be dispensed only from official study sites by authorized personnel according to local regulations.

Vaccine Induction Phase

Patients will receive the first of four induction doses of SurVaxM in emulsion with Montanide and Sargramostim and given every other week on induction cycle 1 week 1, cycle 1 week 3, cycle 2 week 2, cycle 3 week via subcutaneous injection. Patients will receive approximately 500 mcg SurVaxM in 50/50 volume emulsion with Montanide ISA 51 (1 cc total) and a second separate injection of 100 mcg sargramostim in close proximity (1-3 cm) to the first injection.

Vaccine Maintenance Phase

SurVaxM should be administered every 12 weeks (± 2 weeks) after the induction phase until intolerance or tumor progression.

Administration of SurVaxM

SurVaxM must be administered at the clinical trial site by appropriately trained staff.

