9.1 Calendar

9.1 Calenda	Screening -28 days to -1			Cycle 2			Cycle 3 (no vaccine at Wk 3)			Cycle 4+ (every 3 wks from C3 Wk 1	End of Treatment	Post-tx ^I Follow- up	
		Wk 1 D1 ± 3 days	Wk 2 ± 3 days	Wk 3 ± 3 days	Wk 1 D1 ± 3 days	Wk 2 ± 3 days	Wk 3 ±3 days	Wk 1 D1 ± 3 days	Wk 2 ± 3 days	Wk 3 ± 3 days	Wk 1 D1 ± 3 days	At time of discontinuation	30 days post, then q. 8 wks
Treatment													
Pembrolizumab IV ¹		X			X			X			X		
SurVaxM Vaccine ^{2,11}		X induction		X induction		X induction		X induction			X (maintenance)		
Administrative Procedures													
Informed Consent	X												
Inclusion/Exclusion Criteria	X												
Demographics & Medical History	X												
Prior & Concomitant Meds	X												
Post-Study Anti-Cancer Therapy Status	X												
Clinical Procedures/Assessments													
Review of Adverse Events	X	X		X		X		X			X	X	
Physical Exam, including neuro ¹⁰	X	X			X			X			X	X	
Vital Signs and Weight ^{3,10,13}	X	X	X	X	X	X	X	X	X	X	X	X	
ECOG Performance Status	X	X			X			X			X	X	
Laboratory Procedures/Assessments													

Version 9: 1-Nov-2017

Pregnancy Test – urine or	X							X	
serum – HCG ⁴									
PT/INR	X							X	
CBC with Differential ¹⁰	X	X	X		X		X ⁹	X	
CMP ^{5,10}	X	X	X		X		X ⁹	X	
Urinalysis (micro as needed)	X	X	X		X		X	X	
T3, FT4 and TSH	X		X		X		X ⁹	X	
HLA	X								
Efficacy Measurements									
Tumor Imaging ^{6,12}	X						X	X (if longer than 14 days from discontinuation)	
Archival Tissue or Newly Obtained Tissue Collection	X								
Survivin Status -Tissue Sample	X								
Correlative Studies Blood Collection ⁷		X				 	X		
Correlative Studies Blood Collection for [name] Lab for immune-phenotyping ⁸		X	X		X		X		

 $^{^{1}}$ pembrolizumab is given every 3 weeks during the course of the study with window of \pm 2 days in the first 3 cycles and then \pm 5 days. Completion of pembrolizumab Q3W monotherapy consists of 35 treatments (approximately 2 years)

¹¹ Cycle 4+ vaccine will be every 12 weeks

² The vaccine will be given before pembrolizumab. The vaccine is given every 2 weeks x 4 for induction and then every 12 weeks for maintenance. During induction vaccine can be given ± 2 days and then ± 14 days during maintenance.

³ Including blood pressure, respiratory rate, heart rate, temperature, weight, height: height is required at baseline only.

⁴ Serum pregnancy or urine test for women of child-bearing potential.

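### Section 3.2 puts SurVaxM in week 1 of every cycle, which contradicts the four-dose induction and 12-weekly maintenance schedule given everywhere else

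*Combined protocol and SAP*

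**What the plan says.** Section 3.2, under Number of Subjects, contains a dosing rule: "Week 1 of each cycle, the subject will receive both Pembrolizumab and the SurVaxM Vaccine". The next sentence gives SurVaxM alone at cycle 1 week 3 and cycle 2 week 2.

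Three other places describe the vaccine schedule differently from section 3.2 and consistently with each other:

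- **Protocol Summary, Interventions:** "every two weeks for 4 doses and then every 3 months".
- **Section 6.1, Vaccine Induction Phase:** "Patients will receive the first of four induction doses of SurVaxM". The visits listed are cycle 1 week 1, cycle 1 week 3, cycle 2 week 2 and a cycle 3 visit. For maintenance: "SurVaxM should be administered every 12 weeks (± 2 weeks) after the induction phase until intolerance or tumor progression".
- **Section 9.1 calendar:** induction marks at C1 W1, C1 W3, C2 W2 and C3 W1, with the vaccine row empty at C2 W1. Footnote 2: "The vaccine is given every 2 weeks x 4 for induction and then every 12 weeks for maintenance". Footnote 11: "Cycle 4+ vaccine will be every 12 weeks".

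Section 13.0 sets the DLT window at 7 weeks in total. The 10-patient run-in is judged on DLTs in that window.

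**The concern.** For pembrolizumab, week 1 of each cycle is right. For SurVaxM it is right in cycles 1 and 3, wrong in cycle 2, and wrong in most later cycles. A site that applied section 3.2 as written would give a vaccine dose at C2 W1, one week after the C1 W3 dose and one week before the C2 W2 dose.

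That extra dose would fall inside the period that decides whether the run-in passes, so the tolerability being judged would belong to a denser regimen than the one the treatment plan defines. The clinical SurVaxM schedule set out in section 1.3 is the phase I one: four doses at two-week intervals, with three-monthly dosing afterwards for patients who reached six months without progression, serious adverse events or limiting toxicity. It gives no clinical experience at 7-day spacing. In the calendar as it can be read, adverse-event review is marked at the four induction vaccine visits but not at C2 W1, so the extra dose would also come at a visit with no scheduled review.

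**Working it through.** **Inputs.** Cycle length 21 days (section 9.1, footnote 1: pembrolizumab every 3 weeks). SurVaxM dose 500 mcg (Protocol Summary, section 6.1). Visits as listed above. Up to 35 pembrolizumab treatments (sections 3.0, 6.1 and 9.1).

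**Formula.** Study day = (cycle − 1) × 21 + (week − 1) × 7 + 1.

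**Step 1. Reproduce the plan's four doses two weeks apart.** C1 W1 = 1. C1 W3 = 14 + 1 = 15. C2 W2 = 21 + 7 + 1 = 29. C3 W1 = 42 + 1 = 43. The gaps are 14, 14 and 14 days, so the Summary, section 6.1 and the calendar describe the same schedule.

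**Step 2. Apply section 3.2 literally.** Week 1 of cycles 1, 2 and 3 gives days 1, 22 and 43. The vaccine-alone visits give days 15 and 29.

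| | Summary, 6.1, 9.1 | Section 3.2 |
|---|---|---|
| Induction days | 1, 15, 29, 43 | 1, 15, 22, 29, 43 |
| Gaps (days) | 14, 14, 14 | 14, 7, 7, 14 |
| Doses | 4 | 5 |
| Total SurVaxM | 4 × 500 = 2,000 mcg | 5 × 500 = 2,500 mcg |

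**Step 3. Place these in the DLT window.** The second pembrolizumab dose is on day 22, and 22 + 28 = day 50. That is (50 − 1)/7 = 7.0 weeks after day 1, which reproduces the stated 7 weeks. All the doses in the table fall by day 43, so the count is 5 against 4 whether the window closes on day 49 or day 50.

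**Step 4. Follow the rule past induction.** Section 3.2 continues the vaccine at C4 W1, C5 W1 and so on, on days 64, 85, 106 and every 21 days after that. The other sections give 84-day intervals.

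- By day 183, section 3.2 gives week 1 of cycles 1 to 9 (the last on day 169) plus the two extra visits: 9 + 2 = 11 doses. Counting 12 weeks from C3 W1, the other sections give 4 induction doses plus one on day 43 + 84 = 127: 5 doses.
- If all 35 cycles were given, section 3.2 yields 35 + 2 = 37 doses. On the 12-weekly schedule, cycle 35 starts on day 34 × 21 + 1 = 715, and (715 − 127)/84 = 7 further intervals give 8 maintenance doses: 4 + 8 = 12.

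**Step 5. Visit windows.** The gaps above are nominal. Footnote 2 allows ±2 days in induction, while the calendar column headers show ±3 days. At the extremes, the 7-day gap could shrink to 7 − 4 = 3 or 7 − 6 = 1 day, and the 14-day gap to 10 or 8 days. The conclusion does not depend on which window applies.

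**The case against.** The strongest reply is that the operative text is already settled. The sentence sits under Number of Subjects, not in the treatment plan. The Summary, section 6.1 and the calendar agree with each other, and staff schedule visits from the calendar. The full literal reading (37 doses against 12) is so far from the rest that it looks like loose wording a site would be unlikely to follow. Most of this stands, and it is why the practical risk is low. It does not make the sentence correct: it is a current dosing instruction, and I found no statement of which section takes precedence.

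Two further errors might be inferred from the same passages. The documents support neither.

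- **That the DLT window in section 13.0 is miscounted.** A reader might take the first two treatments to mean two visits at which both agents are given together. On the calendar the second such visit is C3 W1 (day 43), and 43 + 28 = day 71 would make the window 10 weeks. Section 13.0 does not require the agents at the same visit. By day 22 a patient on the calendar has had two pembrolizumab doses (days 1 and 22) and two SurVaxM doses (days 1 and 15), so the window works as written.
- **That the plan gives two different maintenance start dates.** The maintenance mark sits in the Cycle 4+ column, which might be read as C4 W1 (week 10). That column covers every later cycle, including C7 W1. Section 6.1 and footnote 2 point to about week 7 + 12 = 19, and a week-10 dose would come only 3 weeks after the fourth induction dose. Naming the first maintenance visit would be a courtesy, not a correction.

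Nor can it be said that 7-day spacing appears nowhere: a mouse experiment in section 1.3 repeated the vaccine every 7 days. What is missing is clinical support.

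**Conclusion.** Section 3.2 is wrong as written about SurVaxM. Its size, if followed, is one extra induction dose (5 against 4, or 500 mcg more) inside the 7-week DLT window, nominal gaps of 7 days where 14 are intended, and 3-weekly instead of 12-weekly vaccine thereafter. This rests on 21-day cycles and on C3 W1 as the fourth induction visit. The text of section 6.1 as I have it shows no week number for that cycle 3 visit, but the calendar and the two-week interval both place it there.

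The point is minor. A reader might infer that run-in patients received the extra dose or that the run-in safety assessment is compromised. Nothing in the documents shows this, and the three consistent sections make it unlikely. The sample size of 41 and the PFS6 rule do not depend on the vaccine schedule.

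**What to change.** Replace the two dosing sentences in section 3.2 with: *Pembrolizumab is given in week 1 of each cycle. SurVaxM is given at C1 W1, C1 W3, C2 W2 and C3 W1, then every 12 weeks (± 2 weeks), per 6.1 and 9.1.*

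The visits should be listed. Simply deleting SurVaxM from the first sentence would leave section 3.2 without the C1 W1 and C3 W1 doses. Because the new text refers to section 6.1, check at the same time that the week number of the cycle 3 induction dose appears there.

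The cost is a wording amendment and a note to sites. The design, the run-in stopping rule, the sample size and the PFS6 analysis stay as they are.
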